Number of Participants with Rationale:	A total of 56 patients are required to detect a minimal clinically important difference in relative change of bone tunnel volume after a 2-year follow-up of 20% given an assumed standard deviation of 25.2% with a power of 0.8 and an α -error of 0.05 and accounting for a drop-out rate of 10% for this equally sized two-group parallel design.
Study Duration:	Expected duration for patient acquisition: 22 months Expected time from first patient acquisition to the end of follow-up of the last patient: 82 months Statistic and Abstract: ca. 6 months
Study Schedule:	First-Patient-In: 07/2017 Last-Patient-Out: 05/2024 Statistics/Abstract: 12/2024
Investigator(s):	PD Dr. med. [name] University Hospital Balgrist
Study Centre(s):	University Hospital Balgrist
Statistical Considerations:	Intention-To-Treat analysis Independent t-test on the primary efficacy outcome comparing the two groups with a significance level of 0.05, 2-sided.
GCP Statement:	This study will be conducted in compliance with the protocol, the current version of the Declaration of Helsinki, the ICH-GCP or ISO EN 14155 (as far as applicable) as well as all national legal and regulatory requirements.

STUDY SUMMARY IN LOCAL LANGUAGE

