11 STATISTICAL METHODS

11.1 Hypothesis

Null hypothesis: Both treatments yield the same relative change in bone tunnel volume from baseline (Visit 2) to follow-up 3 (Visit 5).

$$\mu_{\text{Control}} = \mu_{\text{Intervention}}$$

Alternative hypothesis: The two treatments have a different effect on the primary endpoint after entire follow-up

$$\mu_{\text{Control}} \neq \mu_{\text{Intervention}}$$

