11.2 Determination of Sample Size

For the power calculation a dedicated software (G*Power [84]) was used. It is aimed to detect a 20% difference in relative change of bone tunnel volume between the two groups. Pooling the standard deviations of the percentage volume change of different bone tunnel sections (articular/outside third) and two different tunnels (anteromedial/posterolateral tunnel) from the study conducted by Araki et al. [85] yields an estimate for the overall standard deviation of $\pm 25.175\%$. With a type I error rate of $\alpha=0.05$ and a power of $1-\beta = 0.8$ and assuming both samples to be normally distributed and having equal variances, the required sample size per group is $n = 25$.

Accounting for a drop-out rate of 10% the total number of subjects for equally sized groups to be acquired is $N = 56$.

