11.4 Planned Analyses

In all statistical analyses testing a significant difference in central tendency between the two groups, significance is set at $\alpha = 0.05$. All statistical tests will be two-sided. The results of these tests will be reported in 95% confidence Interval and p-value for the Student's t-test and in Mann-Whitney U and p-value for the Mann-Whitney U test.

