11.4.2 Primary Analysis

Confirmatory analysis is performed on the null hypothesis of equal relative changes in bone tunnel volume from baseline to last CT follow-up (follow-up 3, Visit 5) between the two groups. To make appropriate assumptions on the distribution of the data, the Kolmogorov-Smirnov Test is used to test for significant departure from normality. Significance is set at $\alpha = 0.05$. In case the assumption of normality holds, a Student's t-test is performed to test for a significant difference in means between the two groups. In case the normality assumption is violated, a Mann-Whitney U test is applied. Mean values and standard deviations will be reported. The same procedure will be applied on the dataset of the first CT-follow-up (Visit 4) in the mode of a supportive analysis.

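### A normality pre-test of unstated form selects the primary test, and no comparison analysed by Mann-Whitney has a planned effect estimate with 95% CI

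*Combined protocol and SAP*

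**What the plan says.** - **Synopsis, Statistical Considerations:** "Independent t-test on the primary efficacy outcome comparing the two groups with a significance level of 0.05, 2-sided". No condition is attached.
- **11.4.2 Primary Analysis:** at the 0.05 level, "the Kolmogorov-Smirnov Test is used to test for significant departure from normality". If normality is not rejected, Student's t-test is used; if it is, "In case the normality assumption is violated, a Mann-Whitney U test is applied". The section adds "Mean values and standard deviations will be reported", whichever branch is taken, and carries the same rule over to the Visit 4 data. It does not name the form of the pre-test or the data it is run on. Section 12.2.2 names the software (SPSS) but no variant.
- **11.4 Planned Analyses:** t-test results come with a 95% CI and p-value. Rank-test results are given "in Mann-Whitney U and p-value for the Mann-Whitney U test".
- **11.1 and 11.2:** the null hypothesis, "Both treatments yield the same relative change in bone tunnel volume", is written as equality of two means. The sizing is done "assuming both samples to be normally distributed and having equal variances".
- **Synopsis, Number of Participants:** 20% is the "minimal clinically important difference in relative change of bone tunnel volume".
- **11.4.4:** the radiographic counterpart of the primary outcome gets a t-test with no normality condition.
- **11.4.2.3 to 11.4.2.5:** IKDC and Lysholm follow the gated rule. KT-1000, Lachman, pivot shift and Tegner always go to Mann-Whitney.
- **11.4.2.1:** a secondary ANCOVA selects covariates by p-value (entry below 0.2, removal above 0.05 in a fixed order). No CI is mentioned.

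**The concern.** There are two gaps, and the second matters more.

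First, the confirmatory procedure is not fully determined. Two analysts who both follow 11.4.2 can run different forms of the pre-test, land on different branches, and so test different things: a difference in means or a difference in rank ordering. The hypothesis and the sample size are about means only.

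Second, if the primary outcome goes to Mann-Whitney, the planned inferential output is U and p. Neither says how large the reduction in tunnel widening is, or whether the data are compatible with 20 points. The same reporting rule leaves four secondary outcomes without an interval in every case, and IKDC and Lysholm without one whenever they fail the pre-test. Section 11.4.2.3 itself expects that a ceiling effect may cause this.

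**Working it through.** **Inputs.** From 11.2: difference 20 points, SD 25.175, alpha 0.05 two-sided, power 0.8, drop-out 10%.

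**Step 1, the plan's own figure.** n per group = 2 × (1.960 + 0.842)² × (25.175/20)² = 15.70 × 1.584 = 24.9, so 25. With drop-out, 25/0.9 = 27.8, so 28 per group and 56 in total. The stated figures reproduce. (The exact noncentral t gives 26 per group, and power 0.786 at 25.) The sizing is that of a two-sided comparison of means.

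**Step 2, the interval that would be missing.** Half-width = t(0.975, 48) × SD × √(2/25) = 2.011 × 25.175 × 0.2828 = 2.011 × 7.12 = 14.3 points.

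**Step 3, what the unstated form does.** With mean and SD estimated from the data, the 5% critical distances at n = 25 and n = 50 are 0.264 and 0.188 (plain), and 0.173 and 0.124 (Lilliefors, simulated). Four readings were simulated: plain or Lilliefors, per arm (Mann-Whitney if either arm rejects) or pooled. Each used 25 per arm, SD 25.175 and 20,000 to 40,000 trials per scenario. The two lognormal shapes, centred and scaled to the same SD, are assumptions; the documents give no non-normal shape for this outcome.

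At the 20-point effect:

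| Shape in both arms | Sent to Mann-Whitney, plain | Sent to Mann-Whitney, Lilliefors | Readings reach different verdicts | Power, ungated t | Power, gated rule |
|---|---|---|---|---|---|
| Normal (plan's assumption) | 0% | 5–10% | 1.0% | 78.7% | 78–79% |
| Lognormal, sigma 0.3 | 0.5–0.7% | 22–34% | 4.4% | 78.4% | 78–81% |
| Lognormal, sigma 0.5 | 4–5% | 47–66% | 10.1% | 79.3% | 80–81% plain, 86–89% Lilliefors |

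With no effect the readings reach different verdicts in 0.3%, 1.3% and 2.4% of trials.

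**Step 4, type I error of the gated rule.** With the same shape and variance in both arms it is 4.7–5.3%. With an assumed SD ratio of 1.5 and sigma 0.5 skew it is about 5.4–7.9%, depending on the reading, against about 5% for the t-test.

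**Step 5, the stepwise ANCOVA.** With n = 50, no treatment effect and assumed covariate effects of 0 to 0.5 residual SD per covariate SD, selection by p-value gives a type I error of 5.0–6.4%, against 4.7–5.2% with all four covariates fixed. Fixing them takes the residual df from 48 to 44 and the critical t from 2.011 to 2.015.

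**The case against.** The best defence is that the rule is pre-specified where it counts. Section 11.4.2 is the operative text. It fixes the pre-test, its level and both branches, and its default is the same two-sided t-test as in the synopsis. Gating on normality is dated but conventional. That defence largely stands, and it limits what can be claimed.

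- A reader might infer that the plan contains two rival confirmatory tests. It does not: the synopsis line is a conditional rule cut to its main branch. It needs aligning, but the real ambiguity is the unstated form of the pre-test.
- A reader might take differences in branch as differences in result. At the 20-point effect the four readings fail to pick the same test in 12% of trials (normal), 41% (sigma 0.3) and 70% (sigma 0.5). The verdict changes far less often (Step 3), and the skewed figures rest on assumed shapes.
- A reader might infer that the pre-test inflates the false-positive rate. With a common shape and variance it does not. Inflation appears only when unequal variances and skew are assumed together.
- A reader might infer that no effect could be recovered on the Mann-Whitney branch. Means and SDs are reported on both branches, so a difference and an interval could be worked out afterwards. They are simply not planned.

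Fixed Mann-Whitney tests for KT-1000, Lachman and pivot shift agree with 11.2.1, which labels them non-normal. The choice of test there is not at issue, only what is reported from it.

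Removing the gate also has a real cost: the skewed scenarios in which the ambiguity looks largest are the ones in which a rank test has more power.

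**Conclusion.** The point holds as a gap in planned estimation and a smaller gap in pre-specification. The reporting gap follows from the text alone and needs no simulation: every Mann-Whitney comparison, including the primary one if it takes that branch, has no planned effect estimate with 95% CI. The size of the pre-specification gap depends on the data: negligible to small under the plan's normal assumption, and moderate only if the volume changes are skewed to the degree assumed. Neither gap threatens the 5% level while the arms share shape and variance. The covariate selection in the ANCOVA is minor and does not touch the confirmatory p-value.

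**What to change.** 1. **Section 11.4:** require an effect estimate with 95% CI for every Mann-Whitney comparison. Use the Hodges-Lehmann shift for tunnel volume, IKDC, Lysholm, KT-1000 and Tegner, and the probability of superiority, U/(n1 × n2), for the Lachman and pivot shift grades.
2. **Synopsis and 11.4.2:** name one primary test in both places. This is Student's independent t-test, as in the synopsis and 11.4.4, on mean relative change at Visit 5, with the difference and 95% CI and no normality gate. Keep Mann-Whitney with Hodges-Lehmann as a sensitivity analysis. If the sponsor prefers to keep the gate, its form and the data it is run on must be written down, and item 1 still applies.
3. **Section 11.4.2.1 (minor):** fit the four listed factors as fixed covariates instead of selecting them by p-value.

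The cost is wording only, with no new data and N = 56 unchanged. With normal data no power is lost (78–79% gated or not). If both arms are strongly and equally skewed (sigma 0.5), dropping the gate gives up as much as 9 to 10 points of confirmatory power (79% against 86–89% under Lilliefors), and the sensitivity analysis does not restore it.

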11.4.2.1 Confounder-Controlled Analysis

Additionally to the analysis described above in a secondary analysis, group differences in relative change of bone tunnel volume from baseline to follow-up 2 and from baseline to follow-up 3 are assessed in an analysis of covariance (ANCOVA)-model, controlling for confounding factors. The preliminary model contains the following confounding factors:

- Patient sex [89]
- Patient age [89]
- Preinjury Tegner activity score
- Associated bone/meniscus/cartilage-injury (Present/Not Present)

In a univariate analysis each factor is tested for association with the dependent variable (relative change of bone tunnel volume). All factors with association $p < 0.2$ are then included in a preliminary ANCOVA. A stepwise modelling approach is then used where variables with association $p > 0.05$ are excluded. At each exclusion, the model is computed again. The order of exclusion of all factors not associated significantly with the dependent variable is opposite to the list shown above (i.e. from bottom to top) [90].

11.4.2.2 Secondary Analyses

The procedures described hereafter will be applied on all follow-up datasets. Statistical significance testing is based on the Null hypothesis of both groups having an equal effect on the dependent variables.

11.4.2.3 Patient Subjective Knee Function

Mean values and standard deviations of the two groups at the different follow-up assessments will be reported. Due to the large number of distinct possible outcome values, the outcome of IKDC SKEF and LKSS are treated as continuous data [91]. Group means and standard deviations will be reported. If normal distribution can be assumed – tested with the Kolmogorov-Smirnov Test on an $\alpha = 0.05$ level – an independent-samples Student's t-test will be performed to detect significant differences between the group means. Otherwise – possibly due to a ceiling effect [87] – a Mann-Whitney U test is applied.

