5.2.1 Patient Subjective Knee Function

Patient subjective knee function is assessed using the International Knee Documentation Committee (IKDC) Subjective Knee Evaluation Form (SKEF) and the Lysholm Knee Scoring Scale (LKSS) measured at baseline visit (surgery) and at each follow-up visit.

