6 STUDY DESIGN AND COURSE OF STUDY

6.1 General study design and justification of design

The present study is designed as a randomized patient-blinded equally sized two-group parallel design superiority trial using an active comparator. ACL-reconstruction using the in-house standard of care will be compared to the method under investigation. In a two staged randomization, a total of 56 patients are assigned to either of the two treatment groups.

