11.4.2.4 Assessment of Knee Stability

The side-to-side difference of the KT-1000 Arthrometer Test will be reported in group mean and standard deviation. The two group means will be compared with the Mann-Whitney U test. The side-to-side difference [86] scores of the Lachman Test and the Pivot Shift Test will be reported in frequencies. Statistical inference testing will be done using the Mann-Whitney U test.

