11.4.2.5 Tegner Activity Scale

The difference in TAS scores from baseline (pre-injury state) to follow-up will be reported in group mean and standard deviation. The two groups will be compared using the Mann-Whitney U test.

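### IKDC and Lysholm are compared between arms at follow-up without the Visit 2 score already collected, which gives up some precision and protection against chance imbalance

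*Combined protocol and SAP*

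**What the plan says.** Section 5.2.1 states that IKDC and Lysholm are "measured at baseline visit (surgery) and at each follow-up visit". Section 9.3.2.2 places both questionnaires in the preoperative examination. Under section 9.3.2.3.2 randomisation takes place during the operation, so the Visit 2 scores cannot be affected by the assigned arm.

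Section 11.4.2.2 applies the secondary analyses to every follow-up dataset. For IKDC and Lysholm, section 11.4.2.3 reports group means and standard deviations at each follow-up. If the Kolmogorov-Smirnov test does not reject normality, "an independent-samples Student's t-test will be performed to detect significant differences between the group means"; otherwise a Mann-Whitney U test is used, with a ceiling effect named as a possible reason. Neither a change score nor a covariate is mentioned.

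Tegner is handled differently. Section 11.4.2.5 says: "The difference in TAS scores from baseline (pre-injury state) to follow-up will be reported in group mean and standard deviation". The arms are then compared by Mann-Whitney U, without a covariate.

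The only covariate-adjusted model is the ANCOVA in section 11.4.2.1, which is confined to bone tunnel volume.

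**The concern.** A comparison of follow-up scores alone leaves in the error the part of the between-patient variation that the preoperative score could explain. In any one trial, the same component appears as a carry-over of whatever baseline difference chance has produced between the arms. Sections 6.3.1 and 7.3 describe two blocks of 20 and 36 envelopes and name no stratification factor, so nothing in the allocation balances baseline knee function. With 25 evaluable patients per arm, such a difference need not be small.

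At stake is the width of the interval around the IKDC and Lysholm differences, which bear on whether less tunnel widening is matched by better knee function. If an imbalance appears and adjustment was not prespecified, any later adjustment will look post hoc.

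**Working it through.** **Inputs from the documents.** Section 11.2.1: 25 per group with drop-outs excluded; IKDC difference 11.5, SD 10; Lysholm difference 10, SD 7. Section 11.4: significance level 0.05, and "All statistical tests will be two-sided".

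**Assumed.** The correlation r between baseline and follow-up scores, taken as 0.2, 0.3 and 0.5. Baseline scores come from an injured knee, so a low value is plausible.

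**Step 1: the plan's own figures.** IKDC effect size 11.5/10 = 1.15; the noncentral t at 25 per arm gives power 0.979, against 0.98 stated. Lysholm 10/7 = 1.429 gives 0.999, against 0.99 stated. Both are consistent with the plan.

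**Step 2: precision as planned.** The standard error of the IKDC difference is 10 × √(2/25) = 2.83. With 48 degrees of freedom the 95% half-width is 2.011 × 2.83 = 5.69. For Lysholm, 7 × √(2/25) = 1.98 and the half-width is 3.98.

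**Step 3: precision with the Visit 2 score as covariate.** The residual SD becomes SD × √(1 − r²), with 47 degrees of freedom (multiplier 2.012).

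| r | Variance reduction (r²) | IKDC half-width | Lysholm half-width | IKDC power at 11.5 | IKDC power at 5.75 |
|---|---|---|---|---|---|
| none (as planned) | – | 5.69 | 3.98 | 0.979 | 0.51 |
| 0.2 | 4% | 5.58 | 3.90 | 0.982 | 0.53 |
| 0.3 | 9% | 5.43 | 3.80 | 0.987 | 0.55 |
| 0.5 | 25% | 4.93 | 3.45 | 0.996 | 0.63 |

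These figures treat the baseline slope as known. Estimating it inflates the variance by a factor that averages about 1 + 1/(2n − 4) = 1 + 1/46, or 2%, for a normally distributed covariate. That multiplies the half-widths by √(47/46) = 1.011, so 5.58, 5.43 and 4.93 become about 5.64, 5.49 and 4.98. At r = 0.2 roughly half the gain is spent this way.

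**Step 4: chance imbalance.** The baseline difference between arms has standard error √(2/25) = 0.283 SD, so its 95% range is ±1.96 × 0.283 = ±0.55 SD. With equal SDs at both times, an imbalance at that limit moves the unadjusted IKDC difference by r × 10 × 0.554 = 1.1, 1.7 or 2.8 points for r = 0.2, 0.3 or 0.5.

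This is not a further loss on top of step 3. At r = 0.5 the drop in the squared standard error is 8.0 − 6.0 = 2.0, and the variance contributed by baseline imbalance is 0.5² × 10² × 2/25 = 2.0. They are one component seen in two ways.

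**Step 5: Tegner.** With equal variances σ² at both times, the change score has variance 2σ²(1 − r) and the covariate-adjusted outcome σ²(1 − r²). The ratio of adjusted to plain difference is (1 + r)/2, or 0.60, 0.65 and 0.75 for r = 0.2, 0.3 and 0.5. This is a linear-model result and only a guide for the planned Mann-Whitney test. Regressing the difference on arm and pre-injury score gives the same arm coefficient as regressing the follow-up score on the same two terms, so the outcome can stay as defined.

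**The case against.** Several stronger readings are tempting, and the documents do not support them.

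- **That the tests are invalid or underpowered.** They are not. Unadjusted comparisons are valid under randomisation, and power at the planned differences is already 0.98 or more. At those differences adjustment barely changes it.
- **That all secondary analyses ignore baseline.** Tegner does not. Its outcome is defined in section 5.2.2.4 as the difference from pre-injury, and section 4.3 makes return to the pre-injury level an objective. Subtraction is therefore the question asked, and the criticism is limited to efficiency.
- **That confidence intervals are widened throughout.** Section 11.4 plans a 95% interval only for the t-test; Mann-Whitney results are reported as U and a p-value. The interval argument therefore covers IKDC and Lysholm when normality is accepted, and not the other outcomes.
- **That KT-1000, Lachman and pivot shift need the same change.** These are already differences from the patient's own other knee. Preoperative laxity comes from a torn ligament, and section 7.1.1 makes a positive pivot shift and/or Lachman test an entry condition, which is likely to narrow its spread. Nothing in the documents suggests that it predicts laxity after reconstruction, and ordinal models on three- or four-level grades risk sparse cells at this sample size.

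The remaining objection is that the gain may be small. That stands: at r = 0.2 it is 4% of the variance before the cost of estimating the slope. It limits the weight of the point, but the covariate is already collected and the change costs almost nothing.

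**Conclusion.** The point holds for IKDC and Lysholm as a modest, inexpensive improvement to valid tests. Section 11.4.2.3 leaves out a prerandomisation score that the trial records. The cost is an IKDC half-width of 5.69 points where about 5.58 to 4.93 would be available, for r between 0.2 and 0.5, together with exposure to chance baseline imbalance, which is the same loss in another form.

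The benefit would show in narrower intervals and in differences smaller than planned: at half the planned IKDC difference, power would rise from 0.51 to between 0.53 and 0.63. These sizes rest on an assumed correlation, on the SDs in section 11.2.1 and on a linear relation between baseline and follow-up scores. For Tegner the point is narrower: the planned difference answers the right question, and a covariate would answer it at least as efficiently, apart from the small cost of estimating one slope.

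**What to change.** In section 11.4.2.3, prespecify for each follow-up visit a linear model of the IKDC score, and likewise the Lysholm score, on arm with the patient's Visit 2 score as covariate. Report the adjusted difference with its 95% confidence interval. Retain a fallback: if ceiling effects violate the model, use a rank-based ANCOVA with the same covariate. State how a missing Visit 2 score is handled, because such a patient would otherwise drop out of the model and section 11.5 intends to use all available data.

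In section 11.4.2.5, keep the difference from pre-injury as the Tegner outcome and add the pre-injury score as a covariate, rank-based if needed.

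Leave section 11.4.2.4 as it is. A repeated-measures model across visits is optional; it would need more than one extra parameter because of its visit-specific terms and covariance structure.

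The cost is SAP wording and one degree of freedom per visit-wise model. No new data are needed.
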